### **8.11.2. Additional Analyses of the Primary Efficacy Endpoint**

The primary efficacy outcome will also be assessed separately across the randomization stratification factor of baseline diagnosis (symptomatic cUTI versus AP) for the m-MITT Population. For each baseline diagnosis stratum, a 95% CI will be computed for the difference in the overall success rate using a continuity-corrected Z-statistic. Exploratory analyses in other subgroups may also be conducted.

### **8.11.3. Analysis of Secondary Efficacy Endpoints**

The number and percentage of patients determined to be a clinical cure, clinical failure and indeterminate response at the TOC visit in the MITT, m-MITT, CE and ME Populations will be presented by treatment group. Two-sided 95% CIs for the observed difference in the clinical cure rates between the EXT2514SUL group and the placebo group (background imipenem/cilastatin therapy) will be presented based on a continuity-corrected Z-statistic.

The number and percentage of patients with a per-patient microbiologic eradication, persistence, and indeterminate response at the TOC Visit in the m-MITT and ME Populations will be presented by treatment group. Two-sided 95% CIs for the observed difference in the per-patient microbiological eradication rates between the EXT2514SUL group and the placebo group (background imipenem/cilastatin therapy) will be presented based on a continuity-corrected Z-statistic.

[Redacted content]

  

## 8.12. Safety Analyses

All safety summaries and analyses will be performed on the Safety Population. All patients will be summarized based on the actual treatment received. Safety endpoints include the assessment of TEAEs and the evaluation of changes from baseline in safety laboratory test results, ECGs, vital signs, and physical examinations.

### 8.12.1. Adverse Events

A TEAE is defined as an adverse event occurring on or after the administration of the first dose of study drug. An overview of adverse events will be provided which summarizes the incidence of the following categories:

- All AEs,
- All TEAEs,
- Drug-related TEAEs,
- Mild TEAEs,
- Moderate TEAEs,
- Severe TEAEs,
- SAEs,
- Drug-related SAEs,
- SAE leading to death,
- TEAE leading to discontinuation of study drug, and
- SAE leading to discontinuation of study drug.

Patients with multiple events will be counted only once within each category. Severity grade and relationship will be counted using the maximum severity and the strongest relationship respectively for a patient with multiple TEAEs.

The number and percentage of patients reporting a TEAE in each treatment group will be tabulated by SOC and PT; by SOC, PT, and severity; and by SOC, PT, and relationship (related or unrelated to study drug and imipenem/cilastatin). Summary tables will be presented alphabetically by SOC and decreasing frequency of PT in the EXT2514SUL group within SOC. For all analyses of TEAEs, if the same AE (based on PT) is reported for the same patient more than once, the AE is counted only once for that PT and at the highest severity and strongest relationship to study drug.

The number and percentage of patients reporting a SAE and reporting a TEAE leading to discontinuation of study drug in each treatment group will be summarized by SOC and PT.

A list of patients who have SAEs, a list of patients who discontinue from study drug, and a list of death will be provided. All adverse events will be listed.

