6.2 Screening (-48 hours to Day 1)

Screening can occur up to 48 hours before the first dose of study drug. All Screening procedures must be performed prior to randomization and the first dose of study drug. Screening laboratories will be performed at the local laboratory and may have been collected as standard of care within 48 hours prior to randomization, with the exception of serum creatinine determination, which must be obtained at the local laboratory within 24 hours of the first dose of study drug.

The following procedures will be performed at Screening:

- Obtain informed consent;
- Review all inclusion and exclusion criteria;
- Obtain medical/surgical history, including urological history; record inactive conditions diagnosed within the previous 5 years, complete urological/renal history, and all active conditions;
- Record prior and concomitant medications;
- Obtain demographics, including sex, age, race, and ethnicity;
- Perform a complete physical examination, including height and weight;
- Obtain vital signs, including blood pressure, heart rate, and respiratory rate;
- Assess clinical signs and symptoms;
- Perform pregnancy test for women of childbearing potential only;
- Collect blood samples for serum chemistry, hematology, and blood cultures;
- Collect urine sample by clean-catch midstream or other appropriate method that minimizes risk of bacterial contamination for urinalysis and urine cultures;
- Perform 12-lead ECG and consult the study Medical Monitor and local cardiologist in cases of clinically significant abnormal findings (eg, a QTcF >480 msec); and
- Assess adverse events.

6.3 Treatment Period – Day 1 to Day 14

All patients will receive randomized IV treatment q6h for 7 days (28 doses) or up to 14 days in patients with concurrent bacteremia.

6.3.1 Day 1

The following procedures will be performed at Day 1:

- Obtain vital signs, including blood pressure, heart rate, and respiratory rate;
- Collect PK sample, pre-dose;
- Administer imipenem/cilastatin;
- Collect pre-dose blood samples for:
 - Serum chemistry; and
 - Hematology;
- Collect pre-dose urine sample by clean-catch midstream or other appropriate method that minimizes risk of bacterial contamination for:
 - Urinalysis for all patients; and
 - Urine cultures for any patient who has received a single dose of a short-acting antibiotic in the 24 hours prior to randomization, or for patients who failed preceding antimicrobial therapy;

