8 SAFETY ASSESSMENTS

8.1 Adverse Events

An adverse event is defined as any untoward medical occurrence in a clinical investigation patient administered a pharmaceutical product, which does not necessarily have a causal relationship with this treatment. An adverse event can therefore be any unfavorable and/or unintended sign (including an abnormal laboratory finding), symptom, or disease temporally associated with the use of an investigational medicinal product, whether or not related to the investigational medicinal product. All adverse events, including observed or volunteered problems, complaints, or symptoms, are to be recorded on the appropriate eCRF.

Adverse events, which include clinical laboratory test variables, will be monitored and documented from the time of informed consent until study participation is complete. Subjects should be instructed to report any adverse event that they experience to the Investigator. Beginning at Screening, Investigators should make an assessment for adverse events at each visit and record the event on the appropriate adverse event eCRF.

Wherever possible, a specific disease or syndrome rather than individual associated signs and symptoms should be identified by the Investigator and recorded on the eCRF. However, if an observed or reported sign or symptom is not considered a component of a specific disease or syndrome by the Investigator, it should be recorded as a separate adverse event on the eCRF. Additionally, the condition that led to a medical or surgical procedure (eg, surgery, endoscopy, tooth extraction, or transfusion) should be recorded as an adverse event, not the procedure.

Any medical condition already present at Screening should not be reported as an adverse event unless the medical condition or signs or symptoms present at baseline changes in severity or seriousness at any time during the study. In this case, it should be reported as an adverse event.

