#### **5.2.1. Adverse Events**

An adverse event is defined as any untoward medical occurrence in a clinical investigation patient administered a pharmaceutical product, which does not necessarily have a causal relationship with this treatment. An adverse event can therefore be any unfavorable and/or unintended sign (including an abnormal laboratory finding), symptom, or disease temporally associated with the use of an investigational medicinal product, whether or not related to the investigational medicinal product. All adverse events, including observed or volunteered problems, complaints, or symptoms, are to be recorded on the appropriate electronic case report form (eCRF). Adverse events will be monitored and documented from the time of informed consent until study participation is complete. Adverse events will be coded using the Medical Dictionary for Regulatory Activities (MedDRA, Version 20.0).

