## **8.2. Handling of Dropouts/Missing data**

For the primary efficacy outcome measure of overall response, patients with missing data or who are lost to follow-up will be considered as an indeterminate response and are included in the denominator for the calculation of overall success rate. Thus, patients with an indeterminate outcome are considered as failures for the primary analysis. A clinical failure occurring at an earlier time point will be carried forward to the subsequent visits.

In cases of missing or incomplete dates (e.g. AE and concomitant medications), the missing component(s) will be assumed as the most conservative value possible. For example, AEs with missing start dates, but with stop dates either overlapping into the treatment period or missing, will be counted as treatment-emergent, taking the worst-case approach. When partial dates are present in the data, both a partial start date and/or a partial stop date will be evaluated to determine whether it can be conclusively established that the AE started prior to the start of study drug or ended prior to the start of study drug. If the above cannot be conclusively established based on the partial and/or present dates, then the AE will be considered as treatment-emergent. Actual data values as they appear in the original eCRF will be presented in the data listings.

Missing values for other variables will not be imputed and only observed values will be used in data analyses and summaries.

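### The TEAE definition has no worsening clause, so an adverse event that begins between consent and first dose and then worsens on study drug can fall outside the TEAE tables

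*SAP*

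**What the plan says.** SAP 8.12.1 gives the definition: "A TEAE is defined as an adverse event occurring on or after the administration of the first dose of study drug". Protocol 9.2.4 has the same sentence. Neither document extends it to an earlier event that gets worse.

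SAP 8.2 sets the date rules. For partial dates, the test is whether it can be "conclusively established that the AE started prior to the start of study drug", or that it ended before then. If neither can be shown, the event counts as treatment-emergent. For missing onset, "AEs with missing start dates, but with stop dates either overlapping into the treatment period or missing, will be counted as treatment-emergent".

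Collection starts before dosing. SAP 5.2.1 says: "Adverse events will be monitored and documented from the time of informed consent until study participation is complete". Protocol 6.1 has consent signed at Screening, and Protocol 6.2 says: "Screening can occur up to 48 hours before the first dose of study drug".

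Protocol 8.1 has a rule for pre-existing conditions. A condition already there at Screening is not an adverse event "unless the medical condition or signs or symptoms present at baseline changes in severity or seriousness at any time during the study". It continues: "In this case, it should be reported as an adverse event". SAP 5.2.1 does not repeat this rule.

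**The concern.** The primary objective is the safety profile against placebo, and the TEAE tables are its main summary. A usual definition of treatment-emergent has two limbs: onset after first dose, and worsening after first dose of something already present. Only the first limb is written here.

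The patients are acutely ill at enrolment, so adverse events between consent and dosing are plausible. Suppose a mild event starts a few hours before the first infusion, becomes severe during treatment and leads to stopping study drug. The safety tables should show that course, and it is the one the written rule can leave out. If the question is settled only when cases turn up after unblinding, the classification is open to bias.

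**Working it through.** The documents contain no figure to reproduce, so the check is a reading of the provisions against each other, followed by one scale calculation.

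1. **Does *occurring* include worsening?** The definition does not say *starting*, so this has to be inferred. The causality definitions in Protocol 8.1.3 name occurrence and worsening as two separate things. The TEAE definition names only the first.

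2. **Does onset decide?** SAP 8.2 asks whether the event started, or ended, before study drug. If being ongoing after the first dose were enough, only the *ended* test would be needed. The *started* test has a purpose only if a known pre-dose onset takes an event out of the TEAE set.

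3. **Does the other reading help?** If *occurring* meant present at any time after dosing, every unchanged or resolving pre-dose event would be a TEAE. That does not isolate worsening either, so the definition needs repair on both readings.

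4. **Do the default rules help?** Missing or inconclusive dates default to treatment-emergent. An event with a known pre-dose onset gets no such benefit. An event with a missing start date that continues into treatment is counted, while a properly dated one that worsens on treatment is not.

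5. **Can the situation arise?** Yes. Collection runs from consent, and Screening may open up to 48 hours before the first dose. That is a maximum, and the actual interval may be much shorter.

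6. **Does Protocol 8.1 close the gap?** It opens with conditions already present at Screening. It reaches an event arising between consent and dosing only if Screening is read as the whole pre-dose period, or if its later reference to baseline is read with SAP 8.3 as the last pre-dose assessment. It does not say that the change becomes a new record or which onset date it takes. If the site opens a new record dated at the worsening, that record is a TEAE under the present wording. If the site keeps one record with the true onset, SAP 8.2 excludes it.

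7. **Which outputs are affected?** For the single-record case, these are the overview rows restricted to TEAEs (drug-related, by severity, leading to discontinuation) and the TEAE tables by system organ class and preferred term in SAP 8.12.1. The treatment-emergent SAE table in Protocol 9.2.4 would also omit it if it were serious.

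8. **Scale.** Assume all of about 80 patients, randomized 2:1, are dosed. The arms are then 80 × 2/3 ≈ 53 and 80 × 1/3 ≈ 27. One patient missing from a row lowers it by 1/53 = 1.9 points (ETX2514SUL) or 1/27 = 3.7 points (placebo). The difference, ETX2514SUL minus placebo, falls by 1.9 points in the first case and rises by 3.7 points in the second.

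**The case against.** The strongest defence is that Protocol 8.1 already does the work. The Screening period runs up to Day 1, consent is signed within it, and baseline is the last assessment before dosing. On that reading an event starting hours before the first infusion is present at Screening or baseline. Its worsening must then be reported, and a report dated at the worsening is a TEAE. Protocol 8.1 treats clinically significant laboratory and ECG findings that worsen after Screening in a similar way. The eCRF completion procedures mentioned in Protocol 11.5 are not part of these documents and may settle how records are split.

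This stands in part. It shows that exclusion is not certain, but it rests on a favourable reading of *at Screening* and on an onset-date convention that neither document states.

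The defence is also right that such events do not vanish. They remain in the All AEs row and the listings, and in the SAP's SAE rows if serious, because those rows are not restricted to treatment-emergent events. Stopping study drug appears in disposition by reason (SAP 8.4). Laboratory, vital-sign and ECG changes appear in SAP 8.12.2 to 8.12.4 where relevant.

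A reader might infer that every pre-dose event that worsens is dropped from every TEAE table, or that the rule can only hide drug effects. The documents support neither. The first depends on how the site records the worsening. On the second, the rule applies equally to both blinded arms, and the omitted worsening may be due to the infection or to imipenem/cilastatin.

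**Conclusion.** The point holds in a conditional form. When an adverse event starts between consent and first dose, is kept as one record with a known onset, and worsens on study drug, the written rules leave it out of the TEAE tables. The documents do not say how such an event should be recorded, dated or classified.

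The conclusion rests on reading *occurring* by onset, which SAP 8.2 supports but 8.12.1 does not state, and on the single-record assumption.

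The number of patients affected cannot be estimated, because the documents give neither the frequency of pre-dose adverse events nor the proportion that worsen. The per-patient shifts above show only that, in arms of this size, a single case is visible in a table row. They do not show that a case is likely. The correction is worth making because safety is the primary objective and the change is small.

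**What to change.** In SAP 8.12.1 and Protocol 9.2.4, and in the matching sentence of the protocol synopsis, extend the TEAE definition to an adverse event that starts before the first dose of study drug and worsens in severity or seriousness on or after it.

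In Protocol 8.1 and the eCRF completion instructions, state that such a worsening is entered as a new adverse event record with its own onset date, so that severity, relationship and action taken attach to the on-treatment part. Add a line to SAP 8.2 so that the date rules agree with the extended definition.

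Make the change before unblinding. It costs one clause in each definition, the matching line in SAP 8.2 and one recording instruction. The downside is a slightly higher TEAE count.

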Pharmacokinetic characterization and evaluation of serum exposures of ETX2514SUL in the PK Population will be performed using both non-compartmental and modeling methods. Using a sparse sampling approach, PK samples will be obtained from patients treated with ETX2514SUL or placebo prior to the first dose of study drug on Day 1 (1 sample pre-dose) and at 4 additional time points post-dose on Day 4 (± 1 day) (4 time points post-dose). The PK samples will be collected for both treatment groups to maintain the blind. The PK samples obtained from the ETX2514SUL group will be analyzed using a validated assay by a central bioanalytical laboratory.

Safety:

All patients who receive any amount of study drug (Safety Population) will be included in the safety analyses. Patients who received the wrong study drug for their entire course of treatment will be analyzed in the group based on the drug received.

Adverse events will be coded using version 20.0 (or higher) of the Medical Dictionary for Regulatory Activities. The number and percentage of patients in each treatment group reporting at least 1 occurrence of a TEAE for each unique system organ class and preferred term will be tabulated. A TEAE is defined as an adverse event occurring on or after the administration of the first dose of study drug. Treatment-emergent adverse events will also be tabulated by treatment group, severity, and the relationship to study drug as assessed by the Investigator. The number and percentage of patients in each treatment group reporting at least 1 occurrence of a treatment-emergent serious adverse event will be tabulated. The number and percentage of

TABLE OF CONTENTS

Signature Page	2
Investigator Agreement.....	3
Synopsis	4
Table of Contents.....	15
List of Tables	19
List of Abbreviations and Definition of Terms.....	20
1 Introduction and Background Information	22
1.1 Nonclinical Experience with ETX2514	22
1.2 Clinical Experience with ETX2514	23
1.3 Rationale.....	23
1.4 Risk/Benefit.....	24
2 Study Objectives	25
2.1 Primary Objective	25
2.2 Secondary Objectives	25
2.3 Exploratory Objective	25
3 Study Description.....	26
3.1 Summary of Study Design	26
3.2 Study Indication	27
4 Selection and Withdrawal of Subjects	28
4.1 Inclusion Criteria.....	28
4.2 Exclusion Criteria.....	30
4.3 Withdrawal Criteria.....	32
5 Study Treatments	34
5.1 Treatment Groups.....	34
5.2 Rationale for Dosing	34
5.3 Randomization and Blinding.....	34
5.4 Breaking the Blind	35

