8.3 Serious Adverse Event Reporting – Procedures for Investigators

Initial reports

All SAEs occurring from the time of informed consent until 30 days following the last administration of study drug must be reported to ██████████ Clinical Safety within 24 hours of the knowledge of the occurrence (this refers to any adverse event that meets any of the aforementioned serious criteria). All SAEs that the Investigator considers related to study drug occurring after the 30-day follow-up period must be reported to the Sponsor.

To report the SAE, complete the SAE form electronically in the electronic data capture (EDC) system for the study. When the form is completed, ██████████ Safety personnel will be notified electronically and will retrieve the form. If the event meets serious criteria and it is not possible to access the EDC system, send an e-mail to ██████████ Safety at ██████████ or call the ██████████ SAE hotline (phone number listed below), and fax the completed paper SAE form to ██████████ (fax number listed below) within 24 hours of awareness. When the EDC system becomes available, the SAE information must be entered within 24 hours of the system becoming available.

Safety Contact Information: ██████████ Clinical Safety

██████████ SAE hotline – US:

[contact], dial 3 or [contact], dial 3

[contact] or [contact]

E-mail: ██████████

██████████ SAE hotline – Rest of World:

[contact]

[contact]

E-mail: ██████████

Follow-up reports

The Investigator must continue to follow the subject until the SAE has subsided or until the condition becomes chronic in nature, stabilizes (in the case of persistent impairment), or the subject dies.

Within 24 hours of receipt of follow-up information, the Investigator must update the SAE form electronically in the EDC system for the study and submit any supporting documentation (eg, subject discharge summary or autopsy reports) to ██████████ Clinical Safety via fax or e-mail. If it is not possible to access the EDC system, refer to the procedures outlined above for initial reporting of SAEs.

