9.2.4 Analysis of Safety

All patients who receive any amount of study drug (Safety Population) will be included in the safety analyses. Patients who received the wrong study drug for their entire course of treatment will be analyzed in the group based on the drug received. Safety endpoints include the assessment of TEAEs and the evaluation of changes from baseline in safety laboratory test results, ECGs, vital signs, and physical examinations.

Adverse events will be coded using version 20.0 (or higher) of the Medical Dictionary for Regulatory Activities (MedDRA). The number and percentage of patients in each treatment group reporting at least 1 occurrence of a TEAE for each unique system organ class and preferred term will be tabulated. A TEAE is defined as an adverse event occurring on or after the administration of the first dose of study drug. Treatment-emergent adverse events will also be tabulated by treatment group, severity, and the relationship to study drug as assessed by the Investigator. The number and percentage of patients in each treatment group reporting at least 1 occurrence of a treatment-emergent SAE will be tabulated. The number and percentage of patients (in each treatment group) prematurely discontinuing study drug treatment due to a TEAE will be tabulated by system organ class and preferred term.

Safety laboratory data will be presented by descriptive statistics of the post-baseline value and the change from baseline, as well as the number and percentage of patients with potentially clinically significant laboratory values. Descriptive statistics of vital signs and ECG parameters and the change from baseline will also be presented. An outlier analysis of the ECG parameters will be conducted.

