### **5.2. Safety Assessments**

The safety parameters include the incidence, severity, causality, and seriousness of treatment-emergent adverse events (TEAEs) and the evaluation of changes from baseline in safety laboratory test results, ECGs, vital signs, and physical examinations.

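### SAP 8.12.1 summarizes SAEs without the treatment-emergent limit that the protocol sets, so a pre-dose SAE in a later-dosed patient could be counted under an arm (minor)

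*SAP*

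**What the plan says.** **Protocol.** Section 9.2.4 counts, in each treatment group, the patients "reporting at least 1 occurrence of a treatment-emergent SAE will be tabulated". The synopsis gives the same rule: "reporting at least 1 occurrence of a treatment-emergent serious adverse event will be tabulated".

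**SAP 8.12.1.** The SOC/PT tabulation covers "The number and percentage of patients reporting a SAE and reporting a TEAE leading to discontinuation of study drug in each treatment group". Discontinuations in that sentence are limited to TEAEs; SAEs are not. The overview in the same section has rows for SAEs, drug-related SAEs, SAEs leading to death and SAEs leading to discontinuation, all without the limit, although it has separate rows for all AEs and all TEAEs. The section also gives the dividing line: "A TEAE is defined as an adverse event occurring on or after the administration of the first dose of study drug".

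**Collection.** Recording starts before that line. SAP 5.2.1 says "Adverse events will be monitored and documented from the time of informed consent until study participation is complete". Protocol 8.3 says "All SAEs occurring from the time of informed consent until 30 days following the last administration of study drug must be reported".

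**Population.** SAP 8.12 places every safety summary on the Safety Population, which SAP 7.6 limits to patients who were randomized and received some study drug.

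**The concern.** The protocol and the SAP give different rules for the same table, and the SAP gives no reason for the difference. The missing qualifier is hard to read as shorthand, because SAP 8.12.1 distinguishes AEs from TEAEs elsewhere. A programmer who follows the section as written would include an SAE that began before any study drug was given.

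Safety versus placebo is the primary objective, and the trial is small. If SAEs are few, a single event that cannot be due to study drug could change how the SAE table reads. The SAE row would also not necessarily be a subset of the TEAE row above it in the overview.

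**Working it through.** The plan states no SAE rate, power or alpha, so there is no figure to reproduce. The check is a comparison of the text, followed by arithmetic for scale.

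**1. Which events the two rules treat differently.** An event must meet all of these conditions:
- It starts after consent. The consent form is signed at Screening (Protocol 6.1), and Screening is at most 48 hours before the first dose (Protocol 6.2).
- It is new, or is a change in severity or seriousness of an existing condition. Conditions already present at Screening are otherwise not adverse events (Protocol 8.1).
- It starts before the first dose, so it is not a TEAE.
- The patient is still randomized and dosed, and so is in the Safety Population.

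The SAP wording counts such an event; the protocol wording does not.

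**2. Which rows are exposed.**
- *Drug-related SAEs:* barely. The causality factors in Protocol 8.1.3 expect the event to follow dosing.
- *SAEs leading to discontinuation of study drug:* barely. Study drug must have been started.
- *SAEs leading to death:* only if a patient with a pre-dose SAE was still dosed and later died of it.
- *The plain SAE row and the SAE SOC/PT table:* directly.

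**3. Weight of one patient.** About 80 patients at 2:1 (SAP 4) gives 80 × 2/3 ≈ 53 and 80 − 53 = 27.
- ETX2514SUL: 1/53 = 1.9 percentage points
- Placebo: 1/27 = 3.7 percentage points

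**4. Chance that it happens.** The documents give no pre-dose SAE risk per dosed patient, so *q* is assumed over a range. Expected patients = 80*q*; P(at least one) = 1 − (1 − *q*)^80.

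| Assumed *q* | Expected patients | P(at least one) |
|---|---|---|
| 0.1% | 0.08 | 7.7% |
| 0.5% | 0.4 | 33.0% |
| 1% | 0.8 | 55.2% |
| 2% | 1.6 | 80.1% |

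**5. Direction of the effect.** Pre-dose events cannot depend on study drug, so *q* is taken as equal in both arms. If *p* is the treatment-emergent SAE risk, and the two kinds of event are independent, the risk counted under the SAP wording is 1 − (1 − *p*)(1 − *q*).
- Equal true risks, 4% and 4%: the counted risks stay equal, difference 0 and ratio 1.00.
- Illustrative true risks of 6% and 4% with *q* = 1%: 1 − 0.94 × 0.99 = 6.94% and 1 − 0.96 × 0.99 = 4.96%. The difference goes from 2.0 to 1.98 points, and the ratio from 1.50 to 1.40.

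The expected effect is therefore chance variation plus a modest pull of the ratio towards 1.

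**The case against.** The strongest reply is that the SAP does mean treatment-emergent SAEs. SAP 5.2 names seriousness as an attribute of TEAEs when it lists the safety parameters, and SAP 8.12, which governs 8.12.1, names the assessment of TEAEs as the endpoint. This stands as evidence of intent. It does not settle the wording of 8.12.1, which is the text a programmer follows; it shows that the SAP is inconsistent with itself and supports the correction.

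The route to harm is also narrow. Signs of severe sepsis exclude a patient, expected survival is required (Protocol 4.1 and 4.2), and the window is short. The TEAE tables are correctly restricted. SAEs and all adverse events are listed by patient, so in a trial of this size a pre-dose SAE could be found. All of this stands, and it is why the point is minor.

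A reader might infer more than the documents support:
- *That the tables count every SAE since consent.* The SAP does not say so; the reading comes from a missing qualifier. SAEs in screen failures and undosed patients are outside the Safety Population in any case.
- *That a primary safety comparison is compromised.* None is defined. Safety is the primary objective, but it is summarized descriptively, and the SAE table is one of several outputs.
- *That the arms are compared with bias.* Step 5 shows that no expected difference is created where none exists.
- *That SAE counts will fail to match a table of serious TEAEs.* The SAP plans no such table; its TEAE tables are split by severity and relationship.

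**Conclusion.** The mismatch is real and can be checked from the text, but it is minor. If 8.12.1 is programmed literally, a pre-dose SAE in a patient who is later dosed is counted under an arm, mainly in the plain SAE row and the SAE SOC/PT table. Whether any such event occurs depends on a rate that the documents do not give; the probabilities above show only how the answer moves with the assumption. The conclusion that the effect is noise and dilution rests on pre-dose risk being equal in the two arms, which randomization makes true in expectation. No other analysis in the plan depends on the point.

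**What to change.** In SAP 8.12.1, write treatment-emergent SAE in the four SAE rows of the overview and in the SAE table by SOC and PT, to match Protocol 9.2.4 and the synopsis. Where an onset date is partial or missing, the date rule already in SAP 8.2 decides whether the event is treatment-emergent. Keep all SAEs in the patient listing, with those that start before the first dose flagged as pre-treatment, so that no safety information is lost.

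The cost is a few words in the SAP. Data collection and the protocol are unchanged. The edit should be made before the SAP is final and the blind is broken.
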